5.14 Follow-up assessment

Follow up assessment will comprise four components: (1) the follow up questionnaire, (2) return of a spot (casual) urine sample during week 12 (+/- one week)., (3) collection of home-based BP

Not for Public Circulation or Reproduction

measures during week 12 (+/- one week), and (4) collection of barcodes for all packaged foods and beverages bought into the home for consumption during weeks 11 and 12 (+/- one week)..

Follow up questionnaire

At the end of the 12-week intervention period, participants will be prompted by the study app to complete the follow up questionnaire. Two text reminders will be sent five days apart. If the follow up questionnaire has not been completed within four weeks of the end of the intervention period, then follow up data will be considered missing.

The follow up questionnaire will collect the following information:

- 1. Change in habits regarding salt added to food and/or take away consumption
- 2. Change in the in the number of participants household food is usually purchased for
- 3. Change in body weight (self-reported)
- 4. Use and acceptability of the SaltSwtich smartphone app (intervention group only)
- 5. Use and acceptability of the dietary salt substitute and left-over study salt (intervention group only weighed if possible or estimated if not possible)
- 6. Left-over regular table salt (control group only weighed if possible or estimated if not possible)
- 7. Details of any cardiac event in the past 12 weeks (prompt to complete Serious Adverse Event form if appropriate)
- 8. Number of visits to the Dr and/or hospital during the study period, and number of these visits which are primarily due to their BP or medication for their BP
- 9. Use of meal boxes during the study period e.g. My Food Bag, WOOP.

Collection of BP, urine and packaged food purchases

A spot urine sample (week 12 +/- one week) home-based BP measures (week 12+/- one week), and barcodes for packaged food and beverage purchases (weeks 11 and 12 +/- one week). will be collected as per the baseline phase. Participants will be couriered enough equipment at baseline for collection and return of the second spot urine sample.

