SALTS is a 14-week, two-arm, parallel randomised controlled trial. A two-week baseline period (weeks -2 to -1) will be followed by 12 weeks intervention (weeks 1 to 12) Three hundred and twenty six adults (163 per group) with high BP will be randomised in a 1:1 ratio to receive either the salt reduction intervention (SaltSwitch app + dietary salt substitute) or control (generic information about heart-healthy eating), stratified by ethnicity (Māori and non-Māori) and age (<55yrs and 55yrs+). Randomisation will take place at the end of the baseline phase (beginning of week 1). The primary outcome is 24-hour urinary sodium excretion (mg/day) estimated using a spot (casual) urine sample at week 12. Secondary outcomes are (1) urinary potassium excretion (week 12), (2) average systolic BP (week 12),

Not for Public Circulation or Reproduction

(3) sodium content per 100g of packaged food purchases (week 12), (4) the number of participants achieving BP control (<135/85 mmHg; week 12)[1], and (5) use and acceptability of the SaltSwitch app and dietary salt substitute (week 12). Serious adverse events will be recorded, and if the intervention is effective then cost-effectiveness and cost-utility analyses will also be completed. Both groups will complete home-based BP measures twice per day (morning and evening) in triplicate during weeks -1, 6 and 12; collect a spot (casual) urine sample at weeks -1 and 12; and scan barcodes of all packaged foods purchased for consumption in the home during the 2-week baseline, and during the 2 weeks at the end of intervention (weeks 11 and 12) using a tailored study smartphone application.

Study population and number of participants

Participants will be 326 free-living adults (18yrs+) with high BP who own a smartphone and are willing to do grocery shopping during the study period. A General Practitioner (GP), healthcare provider, or study staff will have confirmed that they have high BP, and \geq 80% will have a recorded systolic BP (SBP) of \geq 140 mmHg at screening. Individuals with high BP and on antihypertensive medication will be eligible since effects of dietary salt reduction are additional to drug therapy[2]. The majority of participants (\geq 70%) will reside in the Auckland region.

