5.18 Secondary outcome measures

- 1. Urinary potassium excretion (mg per day) at week 12
- 2. Average systolic BP at week 12
- 3. Sodium content (mg per 100g) of packaged food purchases (weeks 11 and 12)
- 4. The number of participants achieving BP control (≤135/85 mmHg; week 12)
- 5. Use and acceptability of the SaltSwitch app and salt substitute at week 12 (intervention group only)

Serious adverse events will also be recorded during the trial period. If the intervention is found to be effective cost-effectiveness and cost-utility analyses will also be conducted.

Not for Public Circulation or Reproduction

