8.2.2 Contact for notification of serious adverse events

Participants will be informed on the PIS and consent form that they will be asked to report any SAEs that occurred during the study period, at the end of the study. The RA will report all SAEs immediately to the PI and PM who will then report them in the form of a safety update to HDEC, on a quarterly basis. The PI will have the overall responsibility of ensuring that all events are reported to the regulatory authorities in the appropriate timeframes and that the process is not breached.

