Participants may complete the baseline questionnaire while still on phone call 1 or in their own time. On submission of the baseline questionnaire (when the participant is in a Wi-Fi zone or as data on their phone) the app will link with the on-line database at NIHI and upload the information to secure servers.

Not for Public Circulation or Reproduction

On submission of the baseline questionnaire the study app will also prompt the user to watch three tutorials (BP, urine, and barcode data collection), which they may do during phone call 1, or during their own time. Tutorials will be available to participants via their study app, throughout the entire study period.

Eligible participants will be contacted two weeks after the baseline questionnaire has been completed (allowing time for receipt of the BP monitor) to advise them of the group they have been allocated to. Randomisation will take place at this time. The study app will be activated to send notifications appropriate for their allocated group. Participants allocated to the intervention group will be supported to download and unlock the SaltSwitch app from the app store (iOS or Android) and ensure they can access it via the study app. The SaltSwitch app will prompt the user to complete a short tutorial the first time they open it, which will also be available throughout the entire study period.

Twelve weeks after randomisation participants study apps will prompt them to complete the follow-up questionnaire. The questionnaire will be completed within the secure study app. On submission of the follow-up questionnaire (when the participant is in a Wi-Fi zone or as data on their phone) the app will link with the on-line database at NIHI and upload the information to secure servers. Participants will receive a notification thanking them for their participation, information about their BP over the study etc. The participant will also receive a final email or letter on completion of the study with instructions on how to change SaltSwitch app code and create a Blipcare account for their blood pressure monitor. The participant will also be notified that their blood pressure monitor has been disconnected from the study system. These actions will stop data being sent to the study team, whilst allowing the participant to continue using devices.

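### The only questionnaire item that prompts a serious adverse event form looks back 12 weeks from no fixed date, so a late answer can leave up to the first four intervention weeks uncovered

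*Protocol*

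**What the plan says.** Section 5.14 lists the content of the follow-up questionnaire. Item 7 reads "Details of any cardiac event in the past 12 weeks (prompt to complete Serious Adverse Event form if appropriate"). Items 8 and 9 of the same list (doctor and hospital visits, and meal boxes) refer to the study period as a whole instead.

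On timing, section 5.14 states: "At the end of the 12-week intervention period, participants will be prompted by the study app to complete the follow up questionnaire". Section 11.3 agrees: "Twelve weeks after randomisation participants study apps will prompt them to complete the follow-up questionnaire". The form stays open after that, because follow-up data count as missing only "If the follow up questionnaire has not been completed within four weeks of the end of the intervention period". Late answers are expected: 5.14 provides two text reminders five days apart, and 5.20 allows phone calls if the form is not done within a week of study end.

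On the period for SAEs, section 5.18 states: "Serious adverse events will also be recorded during the trial period". Section 8.2.2 tells participants that "they will be asked to report any SAEs that occurred during the study period, at the end of the study". Section 8.3 says that SAEs are not collected in real time and that all of them are recorded on this questionnaire, with a phone call if needed to complete the information.

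**The concern.** The safety sections promise a fixed period, but the item that collects the events uses a window that moves with the day of answering. Each week of delay removes a week from the start of the intervention and adds a week after its end. The weeks at risk are the earliest after the high-potassium salt substitute is introduced.

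Little else in the plan would pick up an event missed in this way. Non-serious adverse events are not recorded (8.1.1), SAEs are not collected as they occur (8.3), there is no data monitoring committee (8.5), and Table 1 (5.21) places adverse event details at follow-up only. SAE counts could then rest on different stretches of treatment for different participants, without the report showing it.

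**Working it through.** **Inputs.**
- Look-back: 12 weeks, no anchor date (5.14, item 7).
- Prompt: end of the intervention, 12 weeks after randomisation (5.14, 11.3).
- Latest accepted answer: four weeks after the end of the intervention (5.14).
- Trial layout (section 1): "SALTS is a 14-week, two-arm, parallel randomised controlled trial". Of these weeks, the first two are baseline and the other 12 are intervention.

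**The plan's own figure.** 2 baseline weeks + 12 intervention weeks = 14 weeks, as stated. The two extra weeks come before randomisation.

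**Formula.** Put randomisation at time 0 and the end of the intervention at 12 weeks. An answer given L weeks after the prompt, with L from 0 to 4, has the window from L to 12 + L. Intervention time covered is 12 − L weeks. Time missed is L weeks, a share of L/12. Post-intervention time included is also L weeks.

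| Delay L (weeks) | Window (weeks from randomisation) | Intervention weeks missed | Share of 12 weeks |
|---|---|---|---|
| 0 | 0 to 12 | 0 | 0% |
| 1 | 1 to 13 | 1 | 8.3% |
| 2 | 2 to 14 | 2 | 16.7% |
| 3 | 3 to 15 | 3 | 25.0% |
| 4 | 4 to 16 | 4 | 33.3% |

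A participant who answers only after the one-week call in 5.20 is already at the second row or below.

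**Time on the salt substitute.** The salt is couriered after randomisation (5.5), and the delivery time is not given. Assume it arrives 0 to 7 days after randomisation. At the four-week limit (28 days), time on the salt missed is 28 − 7 = 21 to 28 − 0 = 28 days. At one week late it is 0 to 7 days.

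**Baseline.** The two baseline weeks lie outside the window at every L. No salt substitute is in use then, so this is a secondary mismatch with the period promised in 5.18 and 8.2.2, and no loss of exposure time.

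**With a fixed start at randomisation.** Intervention time missed is 0 weeks for every L from 0 to 4.

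**The case against.** The strongest reply is that 5.14 lists topics, not the text shown in the app. The prompt comes exactly 12 weeks after randomisation, so the 12-week phrase plausibly means the intervention period, and the app may display dates. For anyone who answers on prompt the two readings coincide. Reminders and calls shorten delays, and the 33% applies only to an answer on the last accepted day.

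Other routes exist as well. Participants are told they will be asked about any SAE in the study period (8.2.2), Appendix 2 says the questionnaire collects SAEs generally, and 8.3 allows a phone call. Item 8 counts hospital visits over the whole study, and hospitalisation is an SAE criterion (8.2.1).

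Much of this stands. An early event is not certain to be missed, and on-time responders lose nothing. But item 8 carries no prompt to the SAE form, the call in 8.3 serves to complete SAE information, and item 7 is the only listed item that opens the form. These routes lower the risk without settling which period is meant.

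A reader might go further in three ways that the protocol does not support:
- That the 14-week trial length itself costs time on the salt substitute. It does not, because the extra two weeks precede randomisation.
- That delay differs by arm because the intervention group has more items. Controls have their own task, the left-over table salt in item 6, and nothing shows an effect on completion time.
- That post-intervention events will be counted as on-treatment. No section sets such a classification, and the SAE form is not shown.

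**Conclusion.** The point holds as a conditional defect. Taken literally, the item's window can leave out between 0 and 4 of the 12 intervention weeks (0% to 33%), depending on when the participant answers. That contradicts 5.18 and 8.2.2 and is out of step with items 8 and 9.

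The size rests on two assumptions: that the window runs back from the day of answering, since no anchor is given, and that answers are accepted up to the four-week limit. The rate of late completion is not stated, so an expected loss cannot be computed, and 33% is the worst case for one respondent, not an average.

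Item 7 is also limited to cardiac events. That is a separate and larger mismatch with the SAE definition in 8.2.1, and it applies whether or not the answer is on time. Widening the event type alone would leave the moving window in place.

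**What to change.** In item 7, replace the 12-week look-back with a period stated by date: from randomisation, or from consent if baseline events are wanted, to the day of completion. Use the same period in items 7 and 8 and in section 8.2.2, so that the questionnaire and the safety section match. Record the date of each event, so that events before, during and after the intervention can be separated.

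The change is the wording of one item plus a date that the study should already hold. The price is longer recall: 12 + 4 = 16 weeks from randomisation for someone who answers at the limit, and at least 2 + 12 + 4 = 18 weeks if counted from consent. No treatment or clinical rule is affected.

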5.15 Unique study code allocation

Participants will be automatically allocated a unique study code (USC) at referral to enable linkage of information for each participant throughout the trial. USC numbers will be between 00001 and 09999 and allocated randomly. Separate referral and registration numbers will also be allocated to track study numbers at each phase of the trial. All data from the app, including questionnaires and barcodes for shopping purchases, will be exported to protected Drupal database on secure servers at The University of Auckland.

5.16 Physical measurements

Blood pressure, height and weight at screening

Blood pressure, height and weight will be measured at referral by either a trained GP, nurse, pharmacist, or RA. Height will be measured using a standard stadiometer to the nearest 1cm. Blood pressure will ideally be measured seated after 5 minutes rest using an automated BP monitoring device. Three BP measurements will be taken from which the average of the second two measures will be calculated. However, to minimise burden on GPs, nurses, and pharmacists, at least two measures will be enough for referral.

Not for Public Circulation or Reproduction

Urine sample collection

Baseline and follow up spot (casual) urine samples will be collected as described for the baseline phase of the study.

Home based BP measures

Baseline and follow up home-based BP measures will be collected as described for the baseline phase of the study.

5.16 Data collection tutorials

Participants will receive tutorials within the study smartphone app on how to collect BP measures and urine samples, and how to scan the barcodes of packaged foods and beverages bought into the home. A study RA will be available to answer any questions on the tutorials over the phone during the registration phone call, via text message or email. Auckland-based participants who require face-to-face tutorials may be offered these at The University of Auckland Grafton Clinics.

Following the registration phone call and completion of the baseline questionnaire, participants will be couriered a package containing:

- A flow chart showing the processes in the study and the data to collect each week
- Urine collection equipment for 2x spot urine samples
- Wi-Fi enabled BP monitor set up to automatically send readings to University of Auckland servers (via an API)
- Pre-paid courier bags and small bubble-wrapped bags to return tubes containing frozen urine samples (x2)

Following receipt of the package, participants will receive a text from a study RA checking that they are comfortable with how to collect their BP; collect, freeze and courier their urine sample; and collect barcodes for packaged food purchases. The RA will call participants who request support completing the data collection. Participants will also be able to phone, text or email if they have any further questions on how to collect any of the study data.

5.17 Primary outcome measure

24-hour urinary sodium excretion (mg per day) estimated using a spot (casual) urine sample at week 12.

5.18 Secondary outcome measures

- 1. Urinary potassium excretion (mg per day) at week 12
- 2. Average systolic BP at week 12
- 3. Sodium content (mg per 100g) of packaged food purchases (weeks 11 and 12)
- 4. The number of participants achieving BP control (≤135/85 mmHg; week 12)
- 5. Use and acceptability of the SaltSwitch app and salt substitute at week 12 (intervention group only)

Serious adverse events will also be recorded during the trial period. If the intervention is found to be effective cost-effectiveness and cost-utility analyses will also be conducted.

Not for Public Circulation or Reproduction

5.19 Schedule of intervention and follow-up

Participants will be notified by a study RA (via telephone) as to their treatment allocation.

Intervention participants will be sent a text with a link to download the SaltSwitch smartphone app in the iOS or Android app stores, and a code to unlock the app. They will also be sent a supply of study salt (dietary salt substitute) via courier and a link to the intervention tutorial/video (via a notification from the study smartphone app), the latter which will explain how to use the two components of the BP lowering intervention. Intervention participants will receive weekly notifications reminding them to use the SaltSwtich app when shopping for household food, and to use the study salt in place of regular table salt (but not to increase their intake/use of salt).

Control participants will receive one notification at the beginning of the intervention phase (via email) containing a link to information on heart-healthy eating on the Heart Foundation of NZ website, and will be advised not to change their regular salt intake.

At the end of the intervention period participants in the intervention group will receive instructions to ensure they are able to continue using the SaltSwitch smartphone app, but their study data will cease to be collected/recorded in Google Analytics. Control group participants will receive a information on how to download the SaltSwitch app. Both groups will be given information about how to purchase the dietary salt substitute (or a similar product available for sale in New Zealand). Participants will be allowed to keep their BP monitor and will be provided with information on how to download the BP monitor smartphone app to receive a summary of their BP measures collected during the study (and any additional BP measures they collect after study end).

Participants in the intervention group who complete and return their final urine sample will also be eligible to enter a draw to win one of five \$100 grocery vouchers. To enter the draw, participants must indicate your interest on the consent form and complete and return their final urine sample. Winners will be contacted by phone and email at the end of the study (estimated date March 2021). If no response is received within 14 days of notification, another winner will be drawn at random.

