5.5 Randomisation

Eligible participants will be randomised at the beginning of week 1 via a centralised randomisation system. All participants will be randomised in a 1:1 ratio to the intervention or control group, stratified by ethnicity (Māori and non-Māori) and age (<55yrs and 55yrs+) using stratified block randomisation with variable block sizes of two or four.

The RA will activate randomisation for each participant, which will ensure receipt of the correct notifications from the study smartphone app (i.e. intervention or control). The RA will text participants to notify them of the group they have been randomised to and provide the intervention group their SaltSwitch access code. The RA will then call participants in the intervention group to help download and unlock the SaltSwitch app and watch the tutorial. Following the randomisation phone call a study RA will courier a supply of study salt to those in the intervention group.

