5.6 Blinding

It is not possible to blind study participants or researchers to who receives the salt reduction intervention. The study investigators will have no access to treatment allocations during the study. The primary and secondary outcomes will be measured objectively using home-based BP monitors, urine samples and scanned barcodes of packaged foods and beverages purchased, the latter which will be linked to a packaged food composition database to determine the sodium contents.

Not for Public Circulation or Reproduction

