6.2.2 Treatment effects

The primary outcome will be analysed using linear regression model adjusting for baseline outcome value and stratification factors. Model-adjusted mean differences between two groups will be estimated with 95% confidence interval and p-value. Multiple imputation will be used on missing primary outcome data in the primary intention to treat (ITT) analysis; this method creates multiple imputed datasets for incomplete outcome variables that are analysed using same regression models and combined for one inference. The Markov chain Monte Carlo method will be used to produce the parameter estimates, assuming the data are from a multivariate normal distribution and are missing at random. Sensitivity analyses using different assumptions on the missing data, e.g. complete case analysis and last value carried forward, will also be considered to test the robustness of main trial analysis. Per protocol analysis will be performed for participants with no major protocol violations. Generalised linear regression models will be used to analyse secondary outcomes, using a link function appropriate to the distribution of outcome variable. Similar to the primary outcome analysis, the regression model will adjust for baseline outcome value and stratification factors where appropriate. Model-adjusted group differences will be presented with 95% confidence intervals and p-values. For the primary and key secondary outcomes, the heterogeneity of treatment effects between Māori and non-Māori participants will be tested using an interaction term between treatment group and ethnicity in the main model, and also for participants in two different age groups (<55yrs and 55yrs+).

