7.3 Informed consent

Maintenance of confidentiality and compliance with the Privacy Act will be emphasised to all study participants. Participation in the study will be entirely voluntary. A Participant Information Sheet (PIS) and Consent Form will be provided to all eligible potential participants. The consent form will include a question asking participants if they would be happy to be contacted up to two years after the study has finished, to assess longer term outcomes. Participants who do not consent to this question may still take part in the study. Electronic consent will be obtained at the baseline assessment within the study smartphone app. Prior to consent all participants will have had the opportunity to read the PIS and ask questions.

Not for Public Circulation or Reproduction

8. Assessment of Safety / Adverse Event Reporting

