2.1	1.0, 6.2, 6.12 Eligibility criteria	Eligibility criteria at baseline altered: Participants must now have a minimum of 10 rather than 30 scanned barcodes for packaged foods. This was changed to take into account participants who use meal boxes but ensures the technology can still be used.
2.1	6.13, 6.21 Follow up questionnaire	New questions added to follow up questionnaire to assess use of meal boxes (see above), and to collect information for economic analysis (Dr and hospital visits due to high BP or medication for BP).
3.0	1.0, 3.0, 4.0, 5.17, 5.18 Primary outcome 1.0, 6.1 Study power and sample size 5.3, 5.9 Recruitment methods	Study primary outcome changed from Systolic Blood Pressure (SBP) to Dietary Sodium Intake (measured via urinary sodium sample). Secondary outcomes changed accordingly and to include SBP. Study power and sample size revised to reflect change in study primary outcome. Recruitment methods modified to focus on most efficient and productive methods.
3.1	5.11 Changes to referral and screening process due to Covid-19 Appendix 5 – Flow diagram for Covid-19	Due to Covid-19 a remote referral process has been devised so the study can continue.
4.0	Page 5 - Co-ordinating Centre Study Staff (NIHI) 5.19 Schedule of intervention and follow- up	Update of SALTS project team Addition of paragraph on SALTS prize draw for participants who will complete and return their final urine sample

Not for Public Circulation or Reproduction

5.20 Detail of contact points with participants	Fixed wording for sentence 4 onwards of Study end (contact 4 – a. Phone call and b. Email/Letter)

Not for Public Circulation or Reproduction

18. Appendix 5 – Flow Diagram for remote referral and screening option process.

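### As worded, the voucher draw for returning the final urine sample is open to the intervention arm only, an arm-dependent incentive to supply the primary outcome

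*Protocol*

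**What the plan says.** Section 5.19 of the protocol sets up the draw: "Participants in the intervention group who complete and return their final urine sample will also be eligible to enter a draw". The prize is one of five 100-dollar grocery vouchers. No section offers the control group a comparable reward, and no reason is given for limiting it to one arm.

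The sentence that follows names no arm. To enter, "participants must indicate your interest on the consent form and complete and return their final urine sample". Section 7.3 places consent before allocation: "Electronic consent will be obtained at the baseline assessment within the study smartphone app". Section 5.5 then says: "Eligible participants will be randomised at the beginning of week 1 via a centralised randomisation system".

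The rewarded sample is the endpoint. Section 5.17 defines the primary outcome as "24-hour urinary sodium excretion (mg per day) estimated using a spot (casual) urine sample at week 12". Section 5.6 makes the trial open label: "It is not possible to blind study participants or researchers to who receives the salt reduction intervention".

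Section 6.2.2 handles missing primary data by multiple imputation, "assuming the data are from a multivariate normal distribution and are missing at random". It adds sensitivity analyses under other missing-data assumptions and gives complete case and last value carried forward as examples. Section 6.1 plans for a single 10% loss to follow-up, not split by arm.

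Appendix 4 dates the draw to protocol version 4.0, after the Covid-19 changes of version 3.1: "Addition of paragraph on SALTS prize draw for participants who will complete and return their final urine sample". The Overview expected recruitment to begin in May 2019.

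**The concern.** Whatever affects who supplies the primary endpoint should be the same in both arms unless it is part of the treatment under test. The weekly reminders to intervention participants in section 5.19 belong to the treatment. A voucher for posting back a urine tube does not, so this asymmetry can be avoided.

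Participants know their allocation, so an intervention participant has a reason to return the tube that a control does not. If that raises return in one arm, the week-12 comparison may set differently selected groups against each other. A week-12 sample that was never collected cannot be obtained later.

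**Working it through.** **1. The two sentences in section 5.19.** The first limits eligibility to the intervention group. The second has participants opt in on the consent form. Sections 7.3 and 5.5 put consent at baseline and randomisation at the start of week 1, so nobody's arm is known at the opt-in. Read literally, people who later become controls could register interest and then be ineligible. The two sentences fit poorly, and either the restriction or the opt-in wording may be a slip.

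**2. The plan's own sample size.** Inputs from section 6.1: 0.33 SD, SD 1400 mg/day, 80% power, two-sided 5%, 10% loss.
- t-test: 146 per arm; 146 / 0.9 = 162.2, rounded up to 163; total 326, as stated.
- Normal approximation: 145 per arm; 145 / 0.9 = 161.1, rounded up to 162; total 324.
- Power with 163 × 0.9 = 146.7 per arm: 80.7%.
- Target difference: 0.33 × 1400 = 462 mg/day.

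The sample size stands and is not in question.

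**3. When unequal return causes bias.** Arm, baseline sodium and the strata are observed. If return depends only on these, the data are missing at random and the planned imputation is valid even with unequal return. Bias needs a residual gap *g*: non-returners' week-12 sodium minus returners', after allowing for those variables. With the same *g* in both arms and return proportions *p*(I) and *p*(C), each arm's mean is estimated as if its non-returners resembled its returners. Each arm is therefore off by −(1 − *p*) × *g*, and

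bias in (intervention − control) = [*p*(I) − *p*(C)] × *g*.

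The hoped-for effect is negative. If return is better in the intervention arm, a positive *g* pulls the estimate towards the null and a negative *g* exaggerates the benefit.

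**4. Illustration.** The protocol gives no return rate by arm and no value for *g*, so both are assumed. Return of 95% and 85% averages to the planned 10% loss. *g* is 0.25 SD (350 mg/day) or 0.5 SD (700 mg/day). Type I error is for an unadjusted comparison with SD 1400 mg/day.

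| Return I / C | *g* | Shift (mg/day) | Share of 462 | Two-sided type I error |
|---|---|---|---|---|
| 90% / 90% | any | 0 | 0% | 5.0% |
| 95% / 85% | 0.25 SD | 0.10 × 350 = 35 | 8% | 5.5% |
| 95% / 85% | 0.5 SD | 0.10 × 700 = 70 | 15% | 7.1% |
| 90% / 80% | 0.25 SD | 0.10 × 350 = 35 | 8% | 5.5% |
| 90% / 80% | 0.5 SD | 0.10 × 700 = 70 | 15% | 7.0% |

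**5. Dilution.** If only a fraction *f* of participants is exposed to the draw, the shift scales by about *f*. With *f* = 0.5 (assumed), 35 to 70 becomes 17.5 to 35 mg/day. The date of version 4.0 and the number enrolled by then are not given, so *f* is unknown.

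**6. Power.** Unequal return alone costs little: power is 80.6% at 95% / 85% and 78.3% at 90% / 80%, against 80.7% at 90% / 90%. The issue is validity, not precision.

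**The case against.** The strongest reply is that nothing shows any bias. Return that differs by arm is compatible with missing at random. Section 5.20 requires a baseline urine sample, at least six BP readings and 10 scanned items before randomisation, which selects motivated people and supplies baseline sodium for the model. The incentive is small: five vouchers among 163 people is 5 / 163, about a 3% chance, worth about 500 / 163 = 3 dollars in expectation. The draw came late, and entry depends on a consent-form entry that earlier participants may not have made. The restriction may be a wording error. All of this stands, and it limits the likely size. It does not justify leaving a reward for supplying the primary endpoint open to one arm only.

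Two stronger readings are tempting. A reader might infer that the draw guarantees differential missingness that the primary analysis cannot correct. The protocol supports only an unequal incentive, and the planned imputation does correct for unequal return if its assumption holds.

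A reader might also infer a bias of up to a third of the target: 15 points × 1050 mg/day (0.75 SD) = 157.5 mg/day, or 34% of 462. A 15-point difference requires control return of 85% or lower even if every intervention participant returned the sample, and 1050 mg/day would have to be the gap remaining after adjustment. Nothing in the protocol supports those inputs.

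The absence of a named not-at-random analysis is not a fault in itself. Section 6.2.2 gives its sensitivity analyses as examples, and the statistical analysis plan is not at hand.

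**Conclusion.** The point holds as an avoidable asymmetry in how the primary outcome is obtained. Section 5.19 restricts the draw to one arm in plain words, in an open-label trial, for the one sample on which the primary outcome rests, and its own opt-in sentence sits badly with that restriction. If it is a slip, the text needs correcting before anyone follows it literally; if it is deliberate, it should be changed.

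The size and direction of any bias cannot be determined from the protocol. A shift of 35 to 70 mg/day (8 to 15% of 462 mg/day) rests on three assumptions: a 10-point difference in return, a residual gap of 0.25 to 0.5 SD equal in both arms, and all participants exposed. With partial exposure it is smaller, and with no residual gap it is zero. The reason to act is that the asymmetry is cheap to remove and hard to repair afterwards, not that a large bias has been shown.

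**What to change.** - In section 5.19, replace the restriction to the intervention group with *All randomised participants (both groups)*, on identical terms and with the same five vouchers. Reconcile this with the consent-form opt-in.
- Extend the draw to controls still in follow-up.
- Report week-12 urine return by arm, before and after version 4.0.
- If anyone was exposed to the arm-restricted draw, add an arm-specific delta-adjusted (not-at-random) analysis to the sensitivity analyses already planned.

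Cost: the sample size stays at 326 and the number of vouchers does not change. Section 11.2 requires steering committee approval and ethics committee review before the amendment takes effect, and controls need a message. Controls already past week 12 cannot be recovered by the change, which is why the return figures and the extra sensitivity analysis are needed.
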